4.3.1.1.1. Within groups assessment

For each timepoint with blood sample collection for humoral immune response and for RSV-A/B neutralizing titers, the following analysis will be performed by group, using both ED60 and IU/ml unit.

- Percentage of participants with neutralizing titers equal to or above pre-defined assay cut-offs and their 2-sided 95% CIs will be tabulated.
- SRR and 95% CI will be tabulated.
- Unadjusted GMTs and their 95% CIs will be tabulated and displayed graphically.
- The kinetics of unadjusted GMTs will be plotted as a function of time for participants with results available at all timepoints.
- MGIs and their 95% CIs will be tabulated.
- Distribution of neutralizing titers will be displayed using reverse cumulative curves.

4.3.1.1.2. Between groups assessment

The following will be reported for RSV-A/B neutralizing titers:

- The 95% CIs for group GMT ratios and group SRR difference between RSV OA Overseas and RSV OA China at baseline, using both ED60 and IU/ml unit, by the ANCOVA model on log₁₀-transformed titers for each neutralization assay.
- The 95% CIs for group GMT ratios and group SRR difference between RSV OA Overseas and RSV OA China at 6-month after study intervention administration, using both ED60 and IU/ml unit, with the analysis model analogous to the primary analysis.

4.3.1.1.3. Subgroup analysis

The following subgroup analyses will be performed by age categories (60-69, 70-79, ≥ 80 YOA) for RSV-A/B neutralizing titers:

- The 95% CIs for group GMT ratios and group SRR difference between RSV OA Overseas and RSV OA China at baseline, 1-month and 6-month after study intervention administration, using both ED60 and IU/ml unit.
- Unadjusted GMTs and their 95% CIs by group.
- SRR and 95% CI by group.
- MGIs and their 95% CIs by group.

4.3.1.2. Humoral immune response in the immunogenicity subset of RSV OA=ADJ-006 and RSV OA China group

The analysis will be performed on the PPS in the RSV OA China group and the PPS for immunogenicity in the immunogenicity subset of the global study RSV OA=ADJ-006.

The following will be reported for RSV-A/B neutralizing titers using both ED60 and IU/ml unit, with the analysis models/methods analogous to the primary analysis:

- The 95% CIs for group GMT ratios and group SRR difference between RSV OA=ADJ-006 and RSV OA China at 1-month after study intervention administration.

4.3.2. Secondary ARI surveillance (Chinese participants only)

ARI surveillance data are collected from Chinese participants only.

The analysis will be performed on the Exposed Set.

RT-PCR-confirmed RSV A and/or B-associated ARI and LRTD are the cases according to the case definition which have at least 1 sample is tested positive for RSV A and/or B by RT-PCR or equivalent as per the RT-PCR result from nasal/throat swab specimen by site staff or from self-swab taken by the participant.

RSV-confirmed ARI cases and RSV-confirmed LRTD cases will be characterized separately. RSV-confirmed LRTD cases are the LRTD and/or severe LRTD cases evaluated by the adjudication process and confirmed by the results of the RSV RT-PCR.

A case will be considered as RSV positive if the quantitative RT-PCT result is ≥ 726 copies/ml for RSV-A and/or ≥ 704 copies/ml for RSV-B.

The following summaries will be provided by group using the descriptive statistics based on the RSV-confirmed cases:

- The number and percentage of participants who reported 1 or more RSV-confirmed ARI/LRTD cases, RSV-confirmed severe LRTD as per the definitions provided in protocol table 8, during the entire study period (Day 1 up to study end), and those start on or after Day 15 post vaccination up to study end.
- Duration in days of episodes for RSV-confirmed ARI/LRTD cases from Day 15 up to study end, defined as (ARI end date – ARI onset date +1).
- The number and percentage of each of the symptoms/signs associated to RSV-confirmed ARI/LRTD cases from Day 15 up to study end
- The number and percentages of participants with RSV-confirmed ARI/LRTD cases from Day 15 up to study end by intensity (mild, moderate, severe as per protocol table 10)
- The number and percentages of participants with RSV-confirmed ARI/LRTD cases from Day 15 up to study end by frailty status (frail, pre-frail, fit).

Complications and hospitalizations will be summarized by group as:

- The number and percentages of participants with any respiratory and/or non-respiratory complications, for any complications and those related to any RSV confirmed ARI/LRTD episode from Day 15 up to study end.
- The number and percentages of participants with hospitalization related to the RSV confirmed episode from Day 15 up to study end due to respiratory and /or non-respiratory complications.

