To evaluate the humoral immune response in Chinese OA enrolled in the RSV OA group (China) compared to historical data generated in the immunogenicity subset of the global efficacy study RSV OA=ADJ-006.	
 
RSV-A and RSV-B neutralization titres expressed as group GMT ratio (RSV OA=ADJ-006 / RSV OA Vaccine group [China]), 1 month after the RSVPreF3 OA investigational vaccine administration.
 
RSV-A and RSV-B neutralization titres expressed as group SRR difference (RSV OA=ADJ-006 - RSV OA Vaccine group [China]), 1 month after the RSVPreF3 OA investigational vaccine administration.
 

Secondary ARI surveillance (Study participants in China only)	
To describe the RSV-confirmed ARI and RSV-confirmed LRTD in RSV OA Vaccine group (China) and Placebo group (China).	
Occurrence of RT-PCR-confirmed RSV A and/or B-associated ARI and LRTD, according to the case definition**.
 
In study participants in China with RT-PCR-confirmed RSV A and/or B associated ARI and LRTD cases:
 
 
Duration of episodes.
 
Reported symptoms/signs.
 
ARI/LRTD severity.
 
Frailty status.
 

Objectives	Endpoints and estimands
Secondary Safety	

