### 8.2.2.1. Nasal self-swab training with the participant in China

At Visit 1, the study participants in China may be invited to practice a nasal self-swab in the presence of site staff to guide them through the instructions and the procedure. The nasal self-swab training can be repeated at any subsequent visit if the participant raises the need for a new training. This swab should be discarded after the training, it should not be sent to the central laboratory.

ARI surveillance starts on the day of vaccination (Visit 1). If the ARI onset (Day 1) occurs after Visit 3 (Month 6), the ARI procedures will not be conducted.

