### 8.2.2.2. Definitions for ARI surveillance

- **ARI onset (Day 1):** will be defined as the first day when the study participant presents **at least 2 concomitant ARI symptoms/signs meeting the ARI case definition** (see [Table 8](#)). The ARI case must be confirmed by the investigator/site staff or delegate during the ARI visit.

Note: The start and end date of each individual symptom and the presence/absence of each sign will be recorded in the eCRF. It may happen that the start date of an individual symptom/sign is before the ARI onset date, if the first symptom/sign started before the second symptom/sign needed to reach the ARI case definition.

- **ARI end:** will be defined as the first day when all ARI symptoms/signs of the participant have returned to baseline or when they diminished significantly as judged by the investigator.
- **New ARI episode:** An ARI episode will be considered as a new episode only after the resolution of the previous one. Between 2 ARI episodes, there must be at least 7 days free of symptoms/signs (or at baseline level) or at least 7 days with significantly diminished symptoms/signs as judged by the investigator.
- **Complications:** The following complications of interest will be collected through the entire study, starting on the Visit 1. The relationship of these complications to an ARI episode will be assessed by the investigator.
  - **Respiratory complications:**
    - **Pneumonia:** A clinical diagnosis of pneumonia based on signs and symptoms, with or without chest radiograph that demonstrates a new or progressive infiltrate.
    - **New diagnosis of COPD or exacerbation of COPD:** A new diagnosis of COPD or, in a participant with previously diagnosed COPD, a worsening of COPD necessitating to increase the dosage or modify the treatment administered.
    - **New diagnosis of asthma or exacerbation of asthma:** A new diagnosis of asthma or, in a participant with previously diagnosed asthma, a worsening of asthma necessitating to increase the dosage or modify the treatment administered.
    - **Other respiratory complications:** Other diagnosis of respiratory illness, including new diagnosis or exacerbation of a pre-existing respiratory disease (e.g., emphysema, chronic bronchitis).
  - Non-respiratory complications:
    - New onset or worsening congestive heart failure (CHF),
    - Myocardial infarction (MI),
    - Stroke,
    - Diabetes,

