Treatment	Population	Endpoint (Variable)	Intercurrent events (ICEs)		Population level summary
			Description	Handling strategy	
RSVPreF3 OA investigational vaccine at Day 1.	China older adult with ≥ 60 YOA	Occurrence of RT-PCR-confirmed RSV A and/or B-associated ARI and LRTD, according to the case definition. In study participants in China with RT-PCR-confirmed RSV A and/or B associated ARI and LRTD cases: 
 Duration of episodes. Reported symptoms/signs. ARI/LRTD severity. Frailty status. 	Taking prohibited medication /vaccine or intercurrent medical condition during study duration.	All the data collected for the variable of interest are used regardless of whether the intercurrent event occurs (treatment policy strategy).	The percentage of participants by group who report each of the endpoints except duration of episodes. Group mean of duration of episodes

RSV=Respiratory syncytial virus; YOA=Years of age.

The estimands for secondary ARI surveillance is to characterize the RSV-confirmed ARI and LRTD cases in Chinese older adult.

ESTIMANDS FOR SAFETY

The clinical question of interest is to evaluate the safety and reactogenicity after RSVPreF3 OA investigational vaccine administration in vaccinated Chinese older adults.

The estimands for safety evaluation are described in [Table 4](#):

Table 4 Study estimand - secondary safety objective

[figure not shown]
Attributes					
Treatment	Population	Endpoint (Variable)	Intercurrent events (ICEs)		Population level summary
			Description	Handling strategy	

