4.8. Changes to Protocol Defined Analyses

A blinded safety analysis was conducted using data of 11Mar2025 to support the CDE consultation of RSV OA=ADJ-028 study.

There were no other changes or deviations to the originally planned statistical analysis specified in the protocol amendment 1 (Dated: 15 Feb 2024).

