6.3.2. Handling of Partial Dates

When partially completed dates (i.e., dates missing a day and/or month) are used in calculations, the following standard rules will be applied:

- A missing day will be replaced by 15
- A missing day and month will be replaced by June 30th.

The following exceptions apply:

- Adverse events start dates with missing day:
 - If the month is not the same as the vaccine dose, then the imputed start date will be the 1st of the month.
 - If the event starts in the same month as the vaccine dose, the flag indicating if the event occurred before or after vaccination (AE.AESTRTPT) will be used to complete the date. If ‘after study intervention’ is selected, the imputed start date will match the vaccine dose given during that month. If ‘before vaccination’ is selected, the imputed date will be one day before the vaccine dose given during that month.
- Adverse events start dates with missing day and month:
 - If the year is not the same as the vaccine dose, then the imputed start date will be the 1st of January.
 - If the event starts in the same year as the vaccine dose, the flag indicating if the event occurred before or after vaccination (AE.AESTRTPT) will be used to complete the date. If ‘after study intervention’ is selected, the imputed start date will match the vaccine dose given during that year. If ‘before vaccination’ is selected, the imputed date will be one day before the vaccine dose given during that year.
- Adverse event end dates with missing day: the imputed end date will be the last day of the month or the study conclusion date whichever comes first.
- Adverse event end dates with missing day and month: the imputed end date will be the last day of the year (31st of December) or the study conclusion date whichever comes first.

Incomplete ARI onset/end dates will follow the rules analogous to above.

Incomplete concomitant medication/vaccination start/end dates will follow the rules analogous to above with CM.CMENRTPT status “BEFORE” or “ONGOING” status considered.

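### SAP 4.3.2 summarises duration, symptoms/signs, intensity and frailty of RSV-confirmed cases only from Day 15, although the endpoint and the SAP's own estimand set no start day

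*SAP*

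**What the plan says.** **Endpoint and estimand.** Protocol Table 7 has two parts. The first is "Occurrence of RT-PCR-confirmed RSV A and/or B-associated ARI and LRTD, according to the case definition". The second, introduced by "In study participants in China with RT-PCR-confirmed RSV A and/or B associated ARI and LRTD cases", lists duration of episodes, reported symptoms/signs, ARI/LRTD severity and frailty status. SAP 1.1 and SAP Table 3 carry both parts over. None of the three gives a start day, and the case definitions in Protocol Table 8 set no minimum time since vaccination.

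**Collection.** Protocol 8.2.2.1 states that "ARI surveillance starts on the day of vaccination (Visit 1"), so cases in the first two weeks are captured and swabbed.

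**Planned summaries.** SAP 4.3.2 reports participants with RSV-confirmed ARI/LRTD, and with severe RSV-LRTD as defined in Protocol Table 8, over two windows: Day 1 to study end, and onset on or after Day 15 post vaccination. The remaining bullets use the second window only. The first of them reads "Duration in days of episodes for RSV-confirmed ARI/LRTD cases from Day 15 up to study end", and symptoms/signs, intensity by Protocol Table 10 and frailty status carry the same limit. The summaries of RSV-related complications and hospitalisations are also limited to Day 15 onwards.

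**Declared changes.** SAP 4.8 mentions one blinded safety analysis and then says "There were no other changes or deviations to the originally planned statistical analysis".

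**The concern.** The SAP's planned tables do not cover the case population that its own estimand defines. Someone programming from SAP 4.3.2 would produce a Day 1 case count and then four descriptor tables with a smaller denominator, with nothing in the SAP to explain the difference. A confirmed case with onset on Day 10, for example, would appear in the count but not in the duration, symptom, intensity or frailty summaries.

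What is at stake is completeness of a descriptive secondary endpoint. Few confirmed cases are expected, so one or two omitted cases can visibly change a group mean duration or an intensity split.

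**Working it through.** The plan gives no figure to reproduce here. The check is a comparison of text, followed by a rough size.

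**1. Window by item**

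| Item | Protocol Table 7, SAP 1.1, SAP Table 3 | SAP 4.3.2 |
|---|---|---|
| Occurrence of RSV-ARI/LRTD | all confirmed cases | Day 1 and Day 15 windows |
| Severe RSV-LRTD (Protocol Table 8) | not listed by name; bears on severity | Day 1 and Day 15 windows |
| Duration | all confirmed cases | Day 15 only |
| Symptoms/signs | all confirmed cases | Day 15 only |
| Severity, as Protocol Table 10 intensity | all confirmed cases | Day 15 only |
| Frailty status | all confirmed cases | Day 15 only |
| RSV-related complications, hospitalisations | not in the endpoint | Day 15 only |

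Four rows depart from the endpoint: duration, symptoms/signs, intensity and frailty. The occurrence bullet shows that Day 15 is counted from vaccination. In the protocol, Day 15 appears only as the follow-up contact counted from ARI onset, so the cut-off originates in the SAP.

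**2. Share of follow-up.** SAP 6.3.3 numbers the vaccination day as Day 1, so the window is 14 days. Protocol Table 4 plans Visit 3 at 180 days and allows up to 210.

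- 14/180 = 7.8%
- 14/210 = 6.7%

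**3. Expected cases in Days 1 to 14**

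Inputs:
- 1800 participants in China (Protocol 4.1).
- RSV-ARI incidence of 6.7 per 1000 person-years, and a pooled estimate of 16.2 per 1000 persons with upper confidence limit 30.8 (Protocol 2.2).
- RSV season from 1 October to end of April, 212 days (Protocol 8.2.2.3.2).

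The incidence figures are background, not design assumptions. I read all of them as annual, apply them to China, and assume no vaccine effect and no attrition.

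- Flat over the year: 1800 × 14/365.25 × rate = 69.0 × rate
- All incidence in season and the window wholly in season: 1800 × 14/212 × rate = 118.9 × rate

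| Rate per 1000 | Flat, Days 1–14 | In season, Days 1–14 | Flat, Days 1–183 |
|---|---|---|---|
| 6.7 | 0.46 | 0.80 | 6.0 |
| 16.2 | 1.12 | 1.93 | 14.6 |
| 30.8 | 2.13 | 3.66 | 27.8 |

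The last column is 1800 × 183/365.25 × rate. It uses the Day 1–183 safety period of SAP 6.3.4 and is shown for scale.

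**The case against.** **The SAP was free to choose the window.** Protocol 9.3 leaves descriptive ARI analyses to the SAP, and the protocol specifies no ARI analysis window for SAP 4.8 to declare a change from. This stands in part. A reader might infer an undisclosed departure from a protocol analysis, and the documents do not support that. But freedom over method does not shrink a defined endpoint, and SAP 4.3.2 disagrees with SAP Table 3 whatever the protocol delegates. The treatment-policy wording in SAP Table 3 settles nothing either way, because it concerns intercurrent events. The mismatch lies in the variable, which has no start day.

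**Severity is reported early.** This stands. Severe RSV-LRTD, defined by lower respiratory signs or supportive therapy, is counted from Day 1. Only the mild/moderate/severe grading begins at Day 15, so it would be wrong to say that early severity goes unreported.

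**Complications and hospitalisations.** Protocol 8.2.2.2 says "The following complications of interest will be collected through the entire study, starting on the Visit 1", and a reader might infer that the Day 15 limit breaches the endpoint here too. It does not. That sentence governs collection, and these items are not in Protocol Table 7. It is also unclear whether the limit applies to the SAP's row for any complications.

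**Early safety.** Vaccine-associated enhanced disease is a listed pIMD, so a reader might infer that an early safety signal would be hidden. The documents do not support this. An ARI meeting the AE or SAE definition is also reported as such (Protocol 8.2.2.4.1). Inpatient hospitalisation is an SAE criterion (Protocol 10.3.2). SAEs and pIMDs are tabulated for Days 1–183 and listed in detail (SAP 4.3.3.4), and unsolicited AEs are summarised for Days 1–30 (SAP 4.3.3.2). What remains is that these displays are not planned by RSV confirmation.

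**Partial dates.** SAP 6.3.2 says "Incomplete ARI onset/end dates will follow the rules analogous to above". By analogy with the AE rule, an onset with the day missing in the vaccination month could be set to the vaccination date, moving a later case out of the Day 15 tables. This is close to hypothetical. Swabs must fall within 6 days of onset, an ARI reported outside the visit interval is not swabbed, and symptom onset dates are recorded at the call and the visit. A confirmed case with an unknown onset day should be very rare.

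**Conclusion.** The point holds in a narrow form. Followed as written, SAP 4.3.2 does not deliver duration, symptoms/signs, Table 10 intensity and frailty status for RSV-confirmed cases with onset in Days 1 to 14, although Protocol Table 7, SAP 1.1 and SAP Table 3 include those cases. The SAP gives no reason for the cut-off.

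The size is small: about 0.5 to 2 cases at flat incidence and up to about 4 if the window falls in season. These figures depend on the background rates being annual and transferable to China. A vaccine effect or attrition would lower them. The documents do not fix the calendar timing of enrolment, so the in-season figure is an upper illustration. The affected cases stay in the Day 1 count. The endpoint is descriptive, and the co-primary immunogenicity conclusions are unaffected. This is a minor improvement to the plan.

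**What to change.** In SAP 4.3.2, produce the duration, symptoms/signs, intensity and frailty summaries for Day 1 to study end, matching the endpoint and the occurrence bullet. Keep the Day 15 versions as additional tables. The RSV-related complication and hospitalisation summaries lie outside the Table 7 endpoint and can optionally use the same two windows. If they do, the wording should say whether the row for any complications is also limited.

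No change to data collection or to the protocol is needed. The cost is a few lines of SAP text and a few duplicate tables from existing programs.

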6.3.5.2. Duration of events

The duration of an event with a start and end date will be the difference between the start and end date plus one day, i.e., an event that starts on 03MAR2018 and ends on 12MAR2018 has a duration of 10 days.

For solicited administration site and systemic events:

- The duration of a solicited AE with at least one day Grade > 0 is defined as End date(CEENDY) – Start date(CESTDY) + 1, with Start date defined as the first day with the symptom and End date defined as the last day with the symptom in or beyond the solicited period.
- A missing start date will be imputed with the vaccination date.
- For paper diaries, if an ongoing symptom has a missing end date, the end date will be considered equal to vaccination date + 29 days.
- The number of days with grade 3 solicited symptom will be defined considering each day with a known grading=3, irrespective of whether the days are consecutive (if only the max intensity during the ongoing period is recorded and the value is 3, each day of the ongoing period will be counted as grade 3).

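### The SAP's ARI duration formula counts one day too many for episodes with an observed, protocol-defined end date

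*SAP*

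**What the plan says.** SAP section 4.3.2 lists, among the summaries of RSV-confirmed ARI/LRTD cases, the duration of episodes in days, "defined as (ARI end date – ARI onset date +1". The estimand table for ARI surveillance in SAP section 1.1 gives the population-level summary as "Group mean of duration of episodes".

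The two dates in the formula are defined in Protocol section 8.2.2.2:

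- **Onset** "will be defined as the first day when the study participant presents" at least two concurrent qualifying symptoms or signs. This is an ill day.
- **End** "will be defined as the first day when all ARI symptoms/signs of the participant have returned to baseline". The definition has a second part, under which a clear reduction in symptoms also closes the episode, on the investigator's judgement.
- **New episode:** two episodes must be separated by at least 7 days free of symptoms or at baseline level, or by "at least 7 days with significantly diminished symptoms/signs as judged by the investigator".

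SAP section 6.3.5.2 opens with a general rule that duration is end minus start plus one day. Its example is that "an event that starts on 03MAR2018 and ends on 12MAR2018 has a duration of 10 days". For solicited events it then says which end date is meant: "End date defined as the last day with the symptom in or beyond the solicited period".

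The SAP has no ARI end-date definition of its own. Section 6.3.2 deals only with incomplete ARI dates, by analogy with the adverse-event rules. Section 4.8 declares no change from the protocol on this point.

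**The concern.** An inclusive count (end minus start plus one) needs an end date that is itself an ill day. The solicited-event rule has one. The ARI rule appears not to, because the protocol places ARI end on the first day after the episode. The SAP applies the same added day to two end dates that mean different things.

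At stake is the accuracy of a named secondary endpoint, the reported length of RSV-confirmed episodes in the vaccine and placebo groups in China. No hypothesis test, case count or safety result depends on it.

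**Working it through.** **Inputs.** The formula comes from SAP 4.3.2, the onset and end definitions from Protocol 8.2.2.2, and the general duration rule and its example from SAP 6.3.5.2. The documents give no expected episode lengths, so the lengths below are assumed, over a range of 1 to 28 days.

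**Step 1: reproduce the SAP's own example.** 12 March − 3 March + 1 = 9 + 1 = 10 days. This matches the SAP and is right if 12 March is the last day of the event.

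**Step 2: apply the formula to a protocol-defined ARI.** Let an episode last L days with onset on day d.

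- Last episode day: d + L − 1.
- Protocol ARI end (first day outside the episode): d + L.
- SAP 4.3.2: (d + L) − d + 1 = L + 1.
- Without the added day: (d + L) − d = L.

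For example, with onset on 1 March, the last ill day on 7 March and ARI end on 8 March, the SAP gives 8 − 1 + 1 = 8 days for an illness of 7 days.

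| Assumed length L (days) | SAP 4.3.2 | End − onset | Overstatement, 1/L |
|---|---|---|---|
| 1 | 2 | 1 | 100% |
| 3 | 4 | 3 | 33.3% |
| 5 | 6 | 5 | 20.0% |
| 7 | 8 | 7 | 14.3% |
| 10 | 11 | 10 | 10.0% |
| 14 | 15 | 14 | 7.1% |
| 21 | 22 | 21 | 4.8% |
| 28 | 29 | 28 | 3.6% |

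**Step 3: episodes still ongoing at a cut-off.** If the participant is still ill on the date used as the end, that date is an ill day. Seven ill days then end on d + 6, and (d + 6) − d + 1 = 7. Here the added day is right, and dropping it would give 6.

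**Step 4: group means.** Let p be the share of a group's episodes with an observed protocol-defined end, and suppose the remainder are ongoing at the cut-off. The group mean is then overstated by p × 1 day, so by at most one day. The difference between groups moves by the difference between their two values of p. If p is the same in both groups, it does not move: assumed true means of 7 and 10 days become 8 and 11 when p = 1, and the difference is 3 days either way.

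**The case against.** Four arguments can be made for the plan as it stands.

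1. **The formula follows the SAP's general rule.** The opening sentence of SAP 6.3.5.2 is not limited to solicited events, so the ARI line is consistent with the SAP's own convention. That is true, but the convention works only with an inclusive end date, and the protocol's ARI end is exclusive.

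2. **An episode can end with symptoms still present.** Under the second part of the end definition, residual symptoms may remain on the end date, so an inclusive count could be argued for. This has some force clinically. However, the new-episode rule in the same section lets clearly reduced days count towards the gap between two episodes, so by the protocol's own logic they lie outside the episode. That rule was written to separate episodes rather than to count their length, which is one reason for moderate confidence.

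3. **Not every episode has an observed end.** Protocol 8.2.2.4.1 continues follow-up until resolution or study end, and SAP 6.3.2 allows imputed ARI dates, by analogy capped at the study conclusion date. This stands. A reader might infer that every reported duration is one day too long, but the documents do not support that. The added day is right for an episode cut off while ongoing, and with an imputed date the error need not be exactly one day.

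4. **The recorded date may differ from the protocol's definition.** The eCRF captures start and end dates for each symptom, and its completion guidelines are a separate document. If the ARI end date is derived from the last symptomatic day, the added day is correct. In that case the data would depart from Protocol 8.2.2.2 and the SAP should say so, so a clarification is needed either way.

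**Conclusion.** The formula in SAP 4.3.2 does not fit the end date that the protocol defines. For episodes with an observed protocol-defined end it gives one day too many, and group mean durations are overstated by up to one day. On assumed lengths of 5 to 14 days that is 20% to 7% of a single episode's duration.

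A reader might also infer that the comparison between vaccine and placebo is diluted. A ratio of means would move towards 1 (7/10 = 0.700 becomes 8/11 = 0.727), but no ratio or test of duration is planned. The difference in days is essentially unaffected, since the shift is common to observed-end episodes in both groups. The objective is descriptive, concerns participants in China only, and has no bearing on the co-primary tests.

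The conclusion assumes that the ARI end date in the analysis data is the one that Protocol 8.2.2.2 defines, and that a clearly reduced day lies outside the episode, as the new-episode rule implies. Priority is minor and confidence moderate.

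**What to change.** In SAP section 4.3.2:

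- For episodes with an observed protocol-defined end, define duration as ARI end date minus ARI onset date. Equivalently, keep the added day but take the end as the day before the protocol-defined ARI end.
- For episodes still ongoing at the study conclusion or cut-off date used as the end date, keep end minus onset plus one.
- State which count applies when the end date is imputed under section 6.3.2, and note that the ARI rule departs from the general rule in section 6.3.5.2.

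Before finalising, check the eCRF completion guidelines to confirm which day sites enter as ARI end. If it is the last symptomatic day, keep the formula and record the departure from the protocol definition in the SAP.

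The cost is a sentence or two in the SAP and a conditional line in the derivation code. No new data are needed.
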